9.4.4. Clinical Safety Laboratory Assessments

- Refer to [Appendix 2](#) for the list of routine, non-fasting clinical laboratory tests to be performed and to the SoA (Section 2) for the timing and frequency. At the discretion of the investigator, additional samples may be taken for safety reasons.
- Approximately 40 mL (approximately 8 teaspoons [4 teaspoons each for local laboratory and central laboratory assessment]) of whole blood will be collected at Screening and then approximately 10 mL (approximately 2 teaspoons) of whole blood will be collected at each of the other assessment visits for a total of approximately 100 mL (20 teaspoons) over the course of the study
- All protocol-required clinical laboratory samples will be analyzed by a central laboratory contracted by GSK.
- At screening, for prompt assessment of the participant's eligibility local laboratory samples, with the exception of hepatitis B, hepatitis C, and HIV, should be taken and the results received and reviewed prior to randomisation to allow review of exclusion 18. It is important that a sample for analysis by the central laboratory is obtained at the same time and promptly sent to the central laboratory. The local lab results will not be entered into the CRF; however, they will be filed in the respective participant's source documentation.
- The investigator must review the laboratory report (local [as applicable] and central), document this review, and record any clinically relevant changes occurring during the study in the AE section of the CRF. The laboratory reports must be filed with the source documents. Clinically significant abnormal

laboratory findings are those which are not associated with the underlying disease, unless judged by the investigator to be more severe than expected for the participant's condition.

- All laboratory tests with values considered clinically significantly abnormal during participation in the study or within 28 days after the last dose of double-blind study treatment should be repeated until the values return to normal or baseline or are no longer considered significantly abnormal by the investigator or medical monitor. If such values do not return to normal/baseline within a period of time judged reasonable by the investigator, the etiology should be identified and the sponsor notified.
- All protocol-required laboratory assessments, as defined in [Appendix 2](#), must be conducted in accordance with the laboratory manual and the SoA (Section 2).
- If laboratory values from non-protocol specified laboratory assessments performed at the institution's local laboratory require a change in participant management or are considered clinically significant by the investigator, then this should be documented in the source notes, and in the eCRF where applicable (eg, SAE or AE or dose modification).

9.4.5. Medical Problems and Concomitant Medications

Participants will be instructed to record any medical problems they may have experienced and any medications used to treat those problems over the previous 24 hours in the eDiary. These entries will be reviewed by the Investigator/study coordinator at each study visit and recorded in the eCRF as adverse events and concomitant medications as appropriate. Signs and symptoms of COPD should be evaluated according to Section 9.1.2 and Section 12.9.5.

9.5. Pharmacokinetics

- During the 12-Week Double-Blind Treatment Period approximately 2 mL of whole blood samples for measurement of plasma concentrations of nemiralisib will be collected in a subset of randomized participants (approximately 300) at selected sites on days 14 and 28 (total of 12mL) as below:
 - pre-dose (trough)
 - approximately 0-1 hour post dose
 - approximately >1 hour to 6 hours post dose
- Plasma samples will be analyzed to determine plasma pharmacokinetics. Instructions for the collection and handling of biological samples will be provided by the central laboratory. The actual date and time (24-hour clock time) of each sample will be recorded.
- Samples will be used to evaluate the PK of nemiralisib. Samples collected for analyses of nemiralisib plasma concentration may also be used to evaluate safety or efficacy aspects related to concerns arising during or after the study.

- Plasma analysis for nemiralisib will be performed under the control Bioanalysis, Immunogenicity, Biomarkers, BIB /Third Party Resourcing, TPR, GlaxoSmithKline

Drug concentration information that may unblind the study will not be reported to investigative sites or blinded personnel until the study has completed and the database has been unblinded.

9.6. Pharmacodynamics

See Section 9.8, Section 9.9, and Section 10.3.4 for details of pharmacodynamics.

9.7. Genetics

A 6 mL blood sample for DNA isolation will be collected from participants who have consented to participate in the genetics analysis component of the study. Participation is optional. Participants who do not wish to participate in the genetic research may still participate in the study.

In the event of DNA extraction failure, a replacement genetic blood sample may be requested from the participant. Signed informed consent will be required to obtain a replacement sample unless it was included in the original consent.

See [Appendix 6](#) for information regarding genetic research. Details on processes for collection and shipment and destruction of these samples can be found in the Central Laboratory Instruction Manual.

9.8. Biomarkers

- For exploratory research, blood samples will be collected for analysis of selected blood inflammatory biomarkers (including but not limited to high sensitivity C-reactive protein [hs-CRP], chemokine interferon- γ inducible protein 10 kDa (CXCL10)], and procalcitonin) in relation to acute exacerbations of COPD.
- Approximately 20 mL (4 teaspoons) of blood will be collected for all participants at each visit noted in the SoA (Section 2). At Visit 1 (Screening), the sample should be collected as soon as possible after the participant has completed the informed consent, PRO assessments and ECG.
- All biomarker samples will be shipped to the central laboratory contracted by GSK/BIB/TPR, GlaxoSmithKline for analysis and reporting.
- All biomarker assessments must be conducted in accordance with the central laboratory manual.

9.9. Spontaneous Sputum

At Screening and Day 56 only, a spontaneous sputum sample will be collected for all participants who are willing and able to provide spontaneous sputum. Sample collection kits and instructions will be provided by the central laboratory contracted by GSK.

9.10. Health Care Resource Utilization (HCRU) and Health Economics

Participants will record (Yes or No) in the eDiary each day whether or not they have had **any** Unscheduled Health Care Contacts (HCRU) contacts/visits for any reason (including COPD-related and non-COPD-related) other than a scheduled visit to the Investigator's site (this includes contacts/visits with/to a physician's office, visits to urgent care, visits to an emergency department, hospitalizations, and inpatient hospitalization days). For any "Yes" response, participants will be prompted to contact the Investigator to promptly report further details regarding the HCRU and the Investigator will receive an e-mail notification as well. The investigator (or designee) will enter the HCRU details in the eCRF. The investigator (or designee) will ask the participant if any of the health care contacts were due to a COPD exacerbation. The investigator (or designee) could refer to his/her records to verify or supplement information given by the participant, if necessary.

Also, at Visits 2-9 or the Early Withdrawal Visit, the resource utilization data reported by the participant for all health care contacts experienced since the last visit will be reviewed by the investigator (or designee).

All confirmed mild, moderate or severe COPD exacerbations will be recorded in the source document and on the COPD Exacerbation form in the eCRF and on the SAE form in the eCRF (if applicable).

The data collected may be used to conduct exploratory analyses of HCRU and other economic analyses and could include:

- Number of medical care encounters
- Hospitalizations
- Duration of hospitalization (total days or length of stay)
- Re-hospitalization within 30 days
- Number of Emergency Room [ER] visits

9.11. Smoking Cessation Counseling

During Visits 1 through 9 or Early Withdrawal, participants will be given smoking cessation counselling, which includes advice regarding the following:

- the health effects that smoking may cause
- the health benefits that may result if they stop smoking
- if they do not feel capable of discontinuing smoking that their primary care physician may be able to discuss anti-smoking strategies with them
- that they may discontinue smoking at any time during the study and will not have to be withdrawn from the study if they do so.

The specific information to be discussed with each subject is provided in the SRM.

10. STATISTICAL CONSIDERATIONS

The primary objective of this study is to characterize the dose response of nemiralisib when administered in addition to SoC on change from baseline in Clinic Visit FEV₁ at Day 84 (measured at trough and post-bronchodilator), in participants diagnosed with an acute exacerbation of COPD requiring treatment with oral/systemic corticosteroid(s) (prednisone 40 mg/day or equivalent) for 5 days **and** antibiotic(s) for 7 days; the dose and/or duration of prednisone (40 mg/day or equivalent) and/or the antibiotic can be modified according to the Investigator's/medically qualified designee's judgement or according to local country/institution practice. There are initially six doses of nemiralisib to be investigated in this study; however, one additional dose may be included during the course of the study.

A key secondary objective is to evaluate treatment effect of nemiralisib compared with placebo on the rate of subsequent exacerbation(s) (moderate and severe) over the 12-Week Treatment Period. In order to increase precision around the estimate of the treatment effect from a pair-wise comparison of the rate of subsequent exacerbation(s) of COPD, the sample size will be increased for the 750 mcg dose of nemiralisib and placebo.

10.1. Sample Size Determination

The sample size has been determined by considering the probability of achieving the end of study success criteria for both the primary and key secondary objectives.

Assuming a 20% withdrawal rate, approximately 1,250 participants will be randomized in total into the study to ensure approximately 1,000 participants complete the 12-Week Treatment Period.

Initially, the randomization ratio between placebo and the the six doses (12.5 mcg, 50 mcg, 100 mcg, 250 mcg, 500 mcg, and 750mcg) of nemiralisib will be 3:1:1:1:1:3. Randomization will be stratified by index COPD exacerbation severity (moderate or severe) and whether or not the participant will provide PK samples, to ensure a balance across treatments. [Table 2](#) shows the expected sample sizes allocated to the six doses of nemiralisib and placebo at the end of study. These figures are approximate and assume that no further adjustments to the randomization ratio are made. The actual sample sizes at the end of the study may be different, depending upon whether changes are made following the results of the unblinded interim analysis of change from baseline in clinic visit FEV₁.

Table 2 Expected Sample Sizes Allocated to the Five Doses of Nemiralisib and Placebo at the End of the Study

Dose	Number randomized	Number who complete dosing period and provide clinic visit FEV ₁ at Day 84
Placebo	340	272
12.5 mcg	114	91
50 mcg	114	91
100 mcg	114	91
250 mcg	114	91
500 mcg	114	91
750 mcg	340	272

10.1.1. Sample Size for Primary Objective: To Characterize the Dose Response of Nemiralisib when Administered in Addition to SoC on Change from Baseline in Clinic Visit FEV₁ at Day 84

Simulations of change from baseline FEV₁ data have been performed to evaluate the probability of achieving end of study success criteria given the estimated sample size for each dose for various assumed scenarios. Three scenarios were considered, each based on different assumptions of the change from baseline FEV₁ for each of the treatment arms. The scenarios are described in [Table 3](#). The estimate of the dose response profile were obtained from fitting a 3-parameter Emax dose response model to simulated change from baseline FEV₁ data for the expected end of study sample size given these assumed true scenarios. A 3 parameter model was used rather than a 4 parameter model to improve the model convergence under simulation conditions. For the purpose of simulations, a frequentist analysis technique was used which should provide analogous results to fitting non-informative prior distributions for all modelling parameters using a Bayesian framework. A baseline and a single post dose observation were simulated for each subject using the bivariate normal distribution, assuming the between participant standard deviation of 300 mL for both time points, and a correlation of 0.7 between them. The average baseline was considered to be 1.383 L. These values were obtained from the PoC Study PII1116678 (a randomised, double-blind, placebo-controlled, parallel-group, study to evaluate the efficacy and safety of GSK2269557 administered in addition to standard of care in 126 participants diagnosed with an acute exacerbation of COPD). For each simulation, the appropriate number of participants was simulated using the expected sample size completing Day 84 as described in [Table 2](#). For each scenario, 5,000 iterations of simulations were run with each simulation analyzed using proc nlmixed in SAS.

Table 3 Change from Baseline in FEV₁ Assumptions for Three Assumed Scenarios

Dose	Scenario 1	Scenario 2	Scenario 3
Placebo	-20 mL	-20 mL	-20 mL
12.5 mcg	-15 mL	-15 mL	-20 mL
50 mcg	-15 mL	-10 mL	-20 mL
100 mcg	20 mL	10 mL	-15 mL
250 mcg	50 mL	30 mL	-10 mL
500 mcg	80 mL	40 mL	0 mL
750 mcg	80 mL	50 mL	0 mL

Table 4 shows the probability of achieving various criteria under the three assumed scenarios:

Table 4 Probability of Achieving Various Criteria under the Three Assumed Scenarios

Criteria	Scenario 1	Scenario 2	Scenario 3
Observed lowest dose difference from placebo <25 mL ¹	53%	62%	88%
Observing >90% posterior probability that the true difference from placebo for any dose is >0	100%	100%	64%
Observing >90% posterior probability that the true difference from placebo for any dose is >0 with an observed difference from placebo >75 mL ²	97%	44%	0%

1. 25 mL chosen to represent a 'non efficacious' difference from placebo

2. 75 mL chosen to represent a minimum clinically meaningful difference from placebo

The results of the simulations indicate that the proposed sample size and participant allocation to each dose is adequate to achieve the key end of study success criterion for change from baseline FEV₁, where this success is defined as demonstrating >90% posterior probability that the true difference from placebo for any dose of nemiralisib is greater than 0 for the assumptions used and the true response scenarios considered. Although the probability of achieving the key end of success criterion for the primary endpoint is high for scenarios 1 and 2, the true nature of the dose response profile is

currently unknown. In addition to these simulations, consideration of the probability of achieving the end of study success for the secondary endpoint of reduction in exacerbation rate has also been given.

10.1.2. Sample Size for Key Secondary Objective: To Evaluate Treatment Effect of Nemiralisib Compared with Placebo on the Rate of Exacerbations

The key secondary endpoint of number of exacerbations over the 12-Week treatment period will be analysed using a Bayesian generalized linear model assuming a negative binomial distribution for the underlying exacerbation rate. Non-informative prior distributions will be used for all modelling parameters.

The probability of achieving the end of study success criterion for this secondary endpoint was calculated assuming a placebo exacerbation rate of 0.51 per 12 weeks and dispersion parameter of 3.5, observed in the PoC Study PIII16678. With 340 participants in the selected exacerbation dose arm versus 340 participants in the placebo arm, the probability of declaring success (assuming that the true rate reduction over placebo is 25%) is 76%, where success is defined as demonstrating >80% posterior probability that the true rate reduction over placebo is greater than 0%.

Estimates of the variability (dispersion parameter) and placebo exacerbation rate have been taken from PoC Study PIII16678, however have large associated uncertainty. The probability of achieving the end of study success criterion has therefore also been calculated using different assumptions for the dispersion and placebo exacerbation rate and are presented in [Table 5](#). The table shows that the probability of achieving the end of study success criteria for the secondary endpoint varies substantially depending on these assumptions. These assumptions will be assessed during the course of the study.

Table 5 Probability of Achieving the End of Study Success Criterion, Assuming a True Rate Reduction over Placebo of 25% under Different Placebo Exacerbation and Dispersion Assumptions

Placebo Rate	Dispersion Parameter		
	3.5	2	1
0.25	68%	73%	77%
0.51	76%	83%	89%
1.00	81%	90%	96%

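### Table 4, first row (53%, 62%, 88%) is wrong or mislabelled for the current lowest dose, 12.5 mcg: the stated assumptions give about 99% in Scenario 1 and 94-95% in Scenario 2

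*Protocol*

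**What the plan says.** Protocol section 10.1 allocates participants to placebo and "six doses (12.5 mcg, 50 mcg, 100 mcg, 250 mcg, 500 mcg, and 750mcg) of nemiralisib". Table 2 gives the expected Day 84 completers as 272 for placebo, 91 for each dose from 12.5 to 500 mcg, and 272 for 750 mcg. Its title nevertheless reads "Expected Sample Sizes Allocated to the Five Doses of Nemiralisib and Placebo at the End of the Study".

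Section 10.1.1 describes the simulation behind Table 4. A baseline and one post-dose value were drawn per participant, "assuming the between participant standard deviation of 300 mL for both time points, and a correlation of 0.7 between them". A 3-parameter Emax model was fitted to the change from baseline, using the Table 2 completers and 5,000 iterations per scenario.

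Table 3 gives the assumed means. Placebo is -20 mL in every scenario. The two lowest doses read "12.5 mcg -15 mL -15 mL -20 mL" and "50 mcg -15 mL -10 mL -20 mL" for Scenarios 1, 2 and 3.

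The first row of Table 4, "Observed lowest dose difference from placebo" below 25 mL, is 53%, 62% and 88%. A footnote says that 25 mL stands for a non-efficacious difference. The row does not name the dose.

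**The concern.** In Table 3 the true difference between 12.5 mcg and placebo is 5 mL in Scenarios 1 and 2 and 0 mL in Scenario 3, all well below 25 mL. An Emax fit borrows strength from every arm, so the fitted value at so low a dose should seldom exceed 25 mL. A probability of 53% in Scenario 1 would require the typical fitted difference to lie close to the cut. The printed values also differ between Scenarios 1 and 2, although the 12.5 mcg arm has the same mean and the same number of completers in both.

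The row describes how the design behaves at the bottom of the dose range. As printed, it says that in Scenario 1 the lowest dose would look non-efficacious only about half the time.

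**Working it through.** **Inputs.** Completers 272/91/91/91/91/91/272 (Table 2). Means from Table 3. SD 300 mL at both times and correlation 0.7 (section 10.1.1). Cut 25 mL (Table 4).

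**SD of change.** 300 × √(2 × (1 − 0.7)) = 300 × √0.6 = 232.4 mL.

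**Do the other rows of Table 4 reproduce?** Arm means were simulated with these inputs and a 3-parameter Emax model was fitted by weighted least squares. The posterior probability was approximated by a normal distribution for estimate/SE. Converged fits, 4,000 trials per scenario for each of three starting values or parameterisations:

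| Table 4 row | Printed | Recomputed |
|---|---|---|
| >90% probability that any dose difference is >0 | 100 / 100 / 64% | 100 / 100 / 63-67% |
| Same, with observed difference >75 mL | 97 / 44 / 0% | 97 / 45-46 / 0% |

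The method recovers both rows to within about 3 points.

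**First row, fitted difference at 12.5 mcg.**

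| Fit | Scenario 1 | Scenario 2 | Scenario 3 |
|---|---|---|---|
| Printed | 53% | 62% | 88% |
| Profile search over ED50, 20,000 trials | 98.6% | 94.4% | 93.4% |
| Iterative optimiser, converged fits | 98.6-98.7% | 94.6-94.7% | 93.7-96.7% |
| Profile search, baseline-adjusted SD 214.2 mL | 99.2% | 95.7% | 94.4% |

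Tighter lower bounds on ED50 raise these figures (to 99-100%, 95-100% and 99-100%).

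**First row, raw arm difference at 12.5 mcg.** SE = 232.4 × √(1/272 + 1/91) = 28.1 mL.
- Scenarios 1 and 2: Φ((25 − 5)/28.1) = Φ(0.71) = 76%.
- Scenario 3: Φ((25 − 0)/28.1) = Φ(0.89) = 81%.

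Scenarios 1 and 2 must give the same value on this reading, so it cannot produce 53% and 62%.

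**Fitted difference at 50 mcg, same seven-arm design.** Over all fits: 58%, 69%, 89%. Converged or interior fits, with ED50 free or broadly bounded: 54-57%, 64-65%, 88-89%. The closest variant (interior fits, ED50 between 1 and 1,500 mcg) gives 54.4%, 64.0% and 87.7%.

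**Why the two doses differ.** With the Table 3 means entered without sampling noise, the Scenario 1 fit has Emax about 143 mL and ED50 about 267 mcg:
- at 12.5 mcg, 143 × 12.5/(12.5 + 267) = 6.4 mL;
- at 50 mcg, 143 × 50/(50 + 267) = 22.6 mL.

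In Scenario 2 the fitted values are about 5 and 16 mL; in Scenario 3, about 1 and 3 mL. In Scenario 1 only the 50 mcg value lies close to 25 mL, which is what a probability near one half requires.

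**Non-convergence.** About 3%, 13% and 41-49% of the optimiser fits failed in Scenarios 1, 2 and 3. The protocol does not say how such fits were treated.

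**The case against.** The strongest reply is that nothing depends on this row. Section 10.1.1 rests its conclusion on the second row, the success criterion, and that row reproduces. Correcting the first row changes no sample size, allocation, analysis or success rule, and the corrected values make the design look better. This stands, and it limits the weight of the point.

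A reader might infer that 53% was a reason to add 12.5 mcg, or that it argues for opening the 25 mcg arm. The documents do not support that. Section 5.5 justifies 12.5 mcg by its expected target inhibition, the Amendment 02 summary cites full profiling of the dose response, and the 25 mcg option depends on unblinded interim results. None of these passages cites Table 4.

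A reader might also conclude that the row simply is the 50 mcg result. The circumstantial signs are the arm added by Amendment 02, the Table 2 title, and an allocation ratio with six terms for seven arms. But the match is approximate. Over all fits it misses by 5, 7 and 1 points, whereas the Monte Carlo error with 5,000 iterations is about √(0.53 × 0.47/5,000) = 0.7 points. The closer match needs a rule for excluding fits that the protocol does not state. A carry-over is plausible, not shown.

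Scenario 3 is weaker evidence. Up to half of its fits fail, and the 12.5 mcg figure moves with the way they are handled.

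The use of a simpler model is not an error. The protocol discloses that "A 3 parameter model was used rather than a 4 parameter model" and gives convergence as the reason. The Table 2 title is a label slip, since the text above it and the table itself have six doses.

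**Conclusion.** As labelled, the first row of Table 4 contradicts the protocol's own inputs in Scenarios 1 and 2. For 12.5 mcg the probability is about 99% against a printed 53%, and 94-95% against 62%: understatements of about 46 and 32-33 points. Neither the fitted nor the raw reading at 12.5 mcg rescues those two cells. In Scenario 3 the figure is about 93-97% against 88%, a gap of 5 to 9 points that is sensitive to method and should not be pressed.

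This rests on the Table 2 completers, the Table 3 means, an SD of change of 232.4 mL and a 3-parameter Emax fit by least squares. The conclusion for Scenarios 1 and 2 survives baseline adjustment, restriction to converged fits and different ED50 bounds.

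It does not follow that the whole of Table 4 is out of date. Rows two and three hold for the seven-arm design, and they barely change between five and six doses, so they cannot show which design was simulated. The point is a misstated operating characteristic, worth correcting, without a demonstrated effect on conduct or inference.

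**What to change.** Re-run the stated 3-parameter simulation for the seven-arm design and replace the first row of Table 4 with the 12.5 mcg figures. If the row was meant for another dose, label it with that dose instead. In either case, add a sentence on how non-converged fits were counted, and correct the dose count in the Table 2 title. The cost is one simulation run and a table edit, with no change to sample size, allocation or analysis.

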10.2. Populations for Analyses

For purposes of analysis, the following populations are defined:

Population	Description
All Participants Enrolled (APE) Population	All participants who are screened for eligibility
Modified Intent-to-Treat (MITT)	All randomized participants who receive at least one dose of study treatment. Participants will be analyzed according to the treatment that they were randomised to. The MITT Population will be used for all efficacy summaries.
Per-Protocol (PP) Population	The PP population is comprised of the MITT population, excluding any participants with an important protocol deviation. The PP population will be used to present sensitivity analyses for the primary and key secondary efficacy endpoints.
Safety Population	All randomized participants who receive at least one dose of study treatment. Participants will be analyzed according to the treatment they actually received. The Safety Population will be used for all safety summaries.
Pharmacokinetic (PK) Population	All participants in the MITT Population for whom a pharmacokinetic sample was obtained and analyzed. The PK population will be used for all PK summaries.

In the event one or more investigators are withdrawn from the trial due to concerns over protocol deviations, then a further population will be defined, which will consist of all participants in the MITT population excluding participants from those investigators. This population will be used to perform additional sensitivity analysis for the primary and key secondary efficacy endpoints.

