Secondary	
The key secondary endpoint of number of exacerbations (moderate and severe) over the 12-Week treatment period will be analysed using a Bayesian generalized linear model assuming a negative binomial distribution for the underlying exacerbation rate with a log link and an offset to account for the length of time in study for each participant. Non-informative priors will be used for all modelling assumptions. The exacerbation rates for the selected nemiralisib dose and placebo arms, along with the ratio in exacerbation rates nemiralisib/placebo, will be estimated and corresponding 95% credible intervals produced.

Exploratory	Will be described in the RAP

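### The 76% success probability for the key secondary endpoint, and all of Table 5, assume a full 12 weeks from all 340 per arm despite the planned 20% withdrawal; the figures are slightly too high

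*Protocol*

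**What the plan says.** Section 10.1 of the protocol says the sample size was set with both the primary and the key secondary objective in view, and it carries one attrition assumption: "Assuming a 20% withdrawal rate, approximately 1,250 participants will be randomized in total into the study". Table 2 accordingly takes the placebo and 750 mcg arms from 340 randomized to 272 with a Day 84 FEV1.

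Section 10.1.1 uses that loss for the primary endpoint: "the appropriate number of participants was simulated using the expected sample size completing Day 84". Section 10.1.2 does not mention it. The key secondary probability is "calculated assuming a placebo exacerbation rate of 0.51 per 12 weeks and dispersion parameter of 3.5", "With 340 participants in the selected exacerbation dose arm versus 340 participants in the placebo arm", for a true 25% rate reduction, and comes out at 76%. Success means a posterior probability above 80% that the rate is reduced at all. Table 5 varies the placebo rate and the dispersion, but not withdrawal or exposure.

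On the analysis, Section 10.2 states: "The MITT Population will be used for all efficacy summaries". Section 10.3.1 plans a negative binomial model with a log link and "an offset to account for the length of time in study for each participant".

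**The concern.** The analysis model expects unequal follow-up, while the probability calculation appears to give everyone the whole 12 weeks. An offset puts participants with different follow-up on a common rate scale. It does not recover the events that would have been seen in the missing time, so a participant who leaves early carries less information about the rate. If 20% leave before Week 12, the probability of success must be below the value for complete follow-up.

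The exacerbation comparison is the reason these two arms were made three times the size of the others. Section 10.1.2 also says its assumptions will be assessed during the study, so the planning benchmark should reflect the attrition the plan already expects.

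**Working it through.** **Inputs.** 340 per arm, placebo rate 0.51 per 12 weeks, dispersion k = 3.5, rate ratio 0.75 and an 80% posterior threshold (Section 10.1.2); 20% withdrawal (Section 10.1). With a flat prior, the threshold corresponds approximately to a one-sided normal test with z = 0.8416.

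**Formula.** A participant with mean rate r, followed for a fraction t of the 12 weeks, contributes information on the log rate of r·t/(1 + k·r·t). The variance of the log rate ratio is the sum over the two arms of 1/(340 × mean information). The probability of success is Φ(|ln 0.75|/SE − 0.8416), with |ln 0.75| = 0.2877.

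**Step 1: reproduce the stated 76%.** With t = 1 for everyone, the variance is (1/0.51 + 1/0.3825 + 2 × 3.5)/340 = (1.961 + 2.614 + 7)/340 = 0.03405, so SE = 0.1845. Then 0.2877/0.1845 − 0.8416 = 0.717 and Φ = 76.3%, which agrees.

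**Step 2: 20% leave uniformly over 12 weeks.** For a leaver, the average of r·t/(1 + k·r·t) over t from 0 to 1 is (1/k)·[1 − ln(1 + kr)/(kr)].

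- Placebo: a completer contributes 0.1831 and a leaver 0.1218 on average; 0.8 × 0.1831 + 0.2 × 0.1218 = 0.1709.
- Active: a completer contributes 0.1635 and a leaver 0.1044; the mean is 0.1517.
- Variance = (1/0.1709 + 1/0.1517)/340 = 0.0366, SE = 0.1913, and the probability is 74.6%.

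**Step 3: 20% leave uniformly within the first 6 weeks.** The same calculation with t running from 0 to 0.5 gives 73.4%.

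**Step 4: all of Table 5 (%).**

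| Placebo rate | Dispersion | Table 5 | 340, full 12 weeks | 340, uniform withdrawal | 340, withdrawal in first 6 weeks |
|---|---|---|---|---|---|
| 0.25 | 3.5 | 68 | 68.1 | 66.1 | 64.9 |
| 0.25 | 2 | 73 | 72.9 | 70.7 | 69.4 |
| 0.25 | 1 | 77 | 76.9 | 74.5 | 73.1 |
| 0.51 | 3.5 | 76 | 76.3 | 74.6 | 73.4 |
| 0.51 | 2 | 83 | 83.4 | 81.5 | 80.3 |
| 0.51 | 1 | 89 | 89.0 | 87.2 | 86.0 |
| 1.00 | 3.5 | 81 | 81.5 | 80.1 | 79.1 |
| 1.00 | 2 | 90 | 89.7 | 88.4 | 87.4 |
| 1.00 | 1 | 96 | 95.6 | 94.6 | 93.8 |

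The full-exposure column agrees with Table 5 in all nine cells to within rounding. Under either withdrawal pattern every cell is lower, and none rounds to the printed value. The protocol does not say that full exposure was assumed; that is inferred from this match.

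**Step 5: bounds, for reference only.** If withdrawers contributed nothing (272 per arm, full exposure), the base case would be 71.0%. If all 340 were followed but 10% of active-arm time carried no effect, the rate ratio would be 0.9 × 0.75 + 0.1 × 1 = 0.775 and the base case 70.7%.

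**The case against.** The strongest reply is that nothing in Section 10.1.2 is miscalculated: each printed value is right for its inputs, and only a simplifying assumption is left unsaid. That stands as far as it goes. The fault is an omitted design assumption, not a wrong sum.

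It is tempting to infer from the contrast with Section 10.1.1 that 272 should replace 340, which gives 71%. The documents do not support this. The primary endpoint needs a Day 84 FEV1, so completers are the right count there. The rate analysis keeps every randomized and dosed participant for the time observed, so 340 is the right count here.

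A reader might also reach about 71% by supposing that the effect vanishes as soon as treatment stops. The protocol does not say so; Section 4 makes the post-treatment effect an open exploratory question. Nor does Section 10.1.2 say whether the 25% reduction is an on-treatment or an as-randomized effect. If it is the latter, diluting it again would double-count.

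The loss could also be smaller than calculated. Section 8.1 lets participants who stop treatment stay in the study, Section 12.9.4 collects exacerbations to Visit 9, and the 20% is not split between stopping drug and leaving the study. If half of the 20% still contributed full time (an assumption) and the rest left uniformly, the base case would be 75.5%.

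Finally, the shift is small beside the 68–96% range that Table 5 already shows for rate and dispersion, and the protocol sets no minimum probability that 75% would miss. That limits the importance of the point but does not remove it, because those two parameters are varied openly while the expected withdrawal is absent from every cell.

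**Conclusion.** The point holds as a minor correction. Section 10.1.2 and Table 5 have the right number of participants but too much follow-up time, and so overstate the probability of success. In the base case the excess is about 2 points under uniform withdrawal and about 3 points if everyone who withdraws does so in the first 6 weeks. Across Table 5 it is roughly 1 to 2.5 points in the first case and 2 to 4 in the second.

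These sizes rest on a normal approximation with a flat prior, on equal withdrawal in both arms, on withdrawers' data stopping when they leave, and on assumed timing. The documents do not support reading this as an underpowered comparison, as a reason to enlarge the arms, or as grounds for restating the base case at 71%.

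**What to change.** Recompute the base case and all nine cells of Table 5 with 340 per arm and an expected-exposure distribution reflecting 20% withdrawal, and state the timing assumed. Under uniform withdrawal the base case becomes about 75%; early withdrawal (about 73%) can be shown beside it. Say which time the offset counts for participants who stop treatment but remain in the study, so that the calculation and the analysis use the same exposure rule. If a figure near 71% is shown, label it as a worst-case sensitivity.

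The cost is a recalculation and slightly less favourable figures. The sample size, allocation and planned analysis model do not change.
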